14.0 Body Fluid Biospecimens

N/A

15.0 Drug Information

N/A

16.0 Statistical Considerations and Methodology

16.1 Overview

This phase II single arm study will utilize a non-inferiority design approach to assess the rate of major wound complications associated with hypofractionated preoperative radiation therapy of 42.75 Gy in 15 fractions for localized, resectable soft tissue sarcoma of the extremity and superficial trunk compared to conventional fractionation of 50 Gy in 25 fractions.

16.1.1 Primary Endpoint

The primary endpoint of this trial is the proportion of patients who experience major wound complications within 120 days of surgical resection of soft tissue sarcoma of the extremity and superficial trunk following preoperative radiation therapy of 42.75 Gy in 15 fractions. Major wound complication is defined as secondary unplanned operation under general or regional anesthesia for wound repair (e.g., debridement, operative drainage, or secondary wound closure including rotationplasty, free flaps or skin grafts); or wound management without secondary operation including invasive procedures (e.g., aspiration of seroma or readmission for wound care such as intravenous antibiotics or persistent deep packing for 120 days or longer). All patients meeting the eligibility criteria who have signed a consent form and have begun treatment will be evaluable for the primary endpoint.

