4.0 Test Schedule

	Pre-treatment/ Baseline ≤30 days prior to registration	Hypo-fractionated RT 42.75 Gy in 15 fractions	Post-RT Assessment (+/- 5 days)	Pre- Operative Assessment Within 2 weeks of surgery⁹	Post- Operative Assessment 4-8 weeks Post-Surgery^{6,9}	Years 1 & 2 Post-Surgery Assessment Every 6 Months Post-Surgery^{7,8,9} (+/- 8 weeks)	Years 3-5 Post-Surgery Assessment Annually Post- Surgery^{7,8,9} (+/- 8 weeks)
History, physical exam ⁷ , ECOG status	X		X	X		X	X
Pathology review ¹	X				X		
Primary site MRI ² , ⁵	X			X		X	X
PET/CT or CT Chest ⁵ ,	X			X		X	X
Pregnancy test ³	X						
AE Acute Assessment (See section 10.0)	X		X	X			
Hypofractionated RT		X					
CTCAE v5.0 Solicited Late Toxicity Assessment (See section 10.0)	X				X	X	X
Wound Complication Assessment (Appendix VI/Section 11.0)					X	X	
Regional Alopecia Assessment (Appendix V)	X		X	X			
Joint Stiffness Assessment (Appendix IV)	X		X	X		X	X
PROMISE-10 ^a	X			X		X ⁴	
TESS ^b	X			X		X ⁴	

1. Pathology review includes histopathologic diagnosis of soft tissue sarcoma and grade, where applicable.
2. CT is acceptable if MRI is not advisable.
3. For women of childbearing potential only. Must be done ≤7 days prior to beginning radiation treatment. Tubal ligation and IUD in place are exceptions.
4. Obtained at 12, 18, and 24 months.
5. Within 60 days of enrollment
6. Follow Up timepoints may be evaluated outside the anticipated window as deemed appropriate by Stand of Care Radiation Oncology and Orthopedic Surgery follow up schedule
 - a. Patient-Reported Outcomes Measurement Information System
 - b. Toronto Extremity Salvage Score
7. Assessments may be completed by NP/PA in person or by virtual and/or phone visit if patient is unable to return to study site.
8. Per physician discretion
9. If patient develops any type of disease progression or is unwilling to return to the institution, patients will move to yearly survival follow up. No additional assessments will need to be done.

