13.0 Treatment / Follow-up Decision at Evaluation of Patient

As per standard of care, throughout the study, investigators can prescribe any medications/treatments that have been deemed necessary for the well-being and over all treatment of the patient.

- 13.1 A patient is deemed ineligible if after registration, it is determined that at the time of registration, the patient did not satisfy each and every eligibility criteria for study entry. The patient will go off study.
 - If the patient received MR for radiotherapy planning, all data up until the point of confirmation of ineligibility must be submitted.
 - If the patient never received radiation therapy, on-study material must be submitted. No additional follow up is necessary.
- 13.2 Those patients who will not receive any radiation treatment or who will receive radiation treatment elsewhere will go off study.
- 13.3 Inevaluable Patients
If a patient fails to complete radiation therapy for reasons other than toxicity, the patient will be regarded as inevaluable and will be replaced.
- 13.4 Patients with a Major Deviation
A patient is deemed a major violation if:
 - a) PTV_4275 D95% < 90%

AND / OR

b) >25% of PTV_4275 receives $\geq 110\%$ of prescription dose
AND / OR

c) Dose to the organs at risk is more than the recommended limit (Table 2.0)
These patients will be flagged but included in the primary endpoint analysis.
Separate sensitivity analysis will also be performed between the patients with
major violation vs no major violation on major wound complication rate.

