16.2.1 Decision Rule

After the first 108 eligible patients have completed 120 days post-treatment, we'll do the final analysis of the data, and if the Z-test is significant at the 10% significance level, we'll conclude that hypofractionated preoperative radiation therapy of 42.75 Gy in 15 fractions is not inferior to conventional fractionation of 50 Gy in 25 fractions and can be tested further in larger studies.

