16.2.2 Sample Size

This study is expected to need to accrue 108 evaluable patients unless the study is closed early for excessive toxicity. We anticipate approximately 10% lost to follow-up due to 120 day endpoint, therefore we anticipate accruing an additional 12 patients to account for ineligibility, cancellation, or other reasons, making the overall sample size of 120 patients.

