16.2.3 Accrual Rate and Study Duration

The expected accrual rate is about 4 patients per month. With this accrual rate, we expect to finish accrual within about 30 months of study activation, assuming we accrue 120 total patients. The final analysis can begin as soon as the last patient has been observed for 4 months post treatment, or at approximately 3 years after the study opens to accrual.

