16.3.1 Primary Outcome Analysis

16.3.1.1 Definition: The primary endpoint of this trial is the proportion of patients who experience major wound complications within 120 days of surgical resection of soft tissue sarcoma following preoperative radiation therapy. All patients meeting the eligibility criteria who have signed a consent form and have begun treatment will be evaluable for the major wound complication rate.

16.3.1.2 Estimation: The proportion of major wound complications will be estimated by the number of patients who experience the major wound complications within 120 days following surgery divided by the total number of evaluable patients. 95% confidence intervals using normal approximation to binomial wound complication proportion will be calculated.

16.3.1.3 Over Accrual: If more than the target number of patients are accrued, the additional patients will not be used to evaluate the stopping rule or used in any decision making process; however, they will be included in final endpoint estimates and confidence intervals.

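### The written evaluability rule for the primary endpoint counts a patient who is irradiated but never resected as complication-free, which favours non-inferiority and conflicts with the decision-rule and sample-size sections

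*Combined protocol and SAP*

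**What the plan says.** - **Endpoint and evaluable set.** Section 16.1.1 counts major wound complications in the 120 days after resection. It then states: "All patients meeting the eligibility criteria who have signed a consent form and have begun treatment will be evaluable for the primary endpoint". Section 16.3.1.1 repeats the rule.
- **Estimator.** Section 16.3.1.2 takes patients with a complication "within 120 days following surgery divided by the total number of evaluable patients".
- **Replacement.** Section 13.3 says: "If a patient fails to complete radiation therapy for reasons other than toxicity, the patient will be regarded as inevaluable and will be replaced". Section 13.2 takes off study patients who receive no radiation or receive it elsewhere. Neither section mentions a patient who is irradiated and not resected.
- **Decision rule.** Section 16.2.1 runs the test "After the first 108 eligible patients have completed 120 days post-treatment".
- **Extra accrual.** Section 16.2.2 says "We anticipate approximately 10% lost to follow-up due to 120 day endpoint" and adds 12 patients to the 108, also naming ineligibility, cancellation and other reasons.
- **Over-accrual.** Section 16.3.1.3 says of patients beyond the target number that "the additional patients will not be used to evaluate the stopping rule or used in any decision making process".
- **Exit before surgery.** In the section 4.0 schedule, the Pre-Operative Assessment column ("Within 2 weeks of surgery⁹") carries footnote 9, which moves a patient with progression to yearly survival follow-up with no further assessments.

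**The concern.** Only a resected patient can have the event, yet membership of the denominator is fixed when radiation begins. Between the two, a patient can progress, decline surgery, become unfit or die, and footnote 9 shows that the protocol foresees exits at this stage. As written, such a patient is evaluable and contributes a zero.

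The direction is known. There is no control arm to be diluted in parallel, so every such zero moves the observed rate away from the 45% ceiling and toward a claim of non-inferiority. That is the error the one-sided 10% level is meant to limit. If the denominator is settled only after the data are seen, the same events can also give either decision.

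**Working it through.** **Inputs.** From section 16.2: 108 evaluable patients, null rate 0.45, alternative 0.35, one-sided level 0.10, Z-test with the standard error at the null. From section 16.2.4: power 80.01%. The number of unresected patients among the 108, k, is not in the documents; k = 0 to 5 is an assumption.

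**Step 1: reproduce the design.** n = [1.2816·√(0.45·0.55) + 0.8416·√(0.35·0.65)]² / 0.10² = 107.95, which rounds up to 108. Normal-approximation power at 108 is 80.01%. Inflation: 108/(1 − 0.10) = 120. The plan's figures are right.

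**Step 2: find the cut-off.** z(x, n) = (x/n − 0.45)/√(0.45·0.55/n), and the test passes if z ≤ −1.2816.
- 41 of 108: z = −1.470, pass.
- 42 of 108: z = −1.277, fail.

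The trial therefore passes at 41 or fewer. Exact type I error is P(Bin(108, 0.45) ≤ 41) = 0.084, and exact power at 0.35 is 0.774.

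**Step 3: put k unresected patients in the denominator.** Only 108 − k patients can have an event, but the cut-off stays at 41 of 108. With a true rate of 45% among resected patients:
- written rule: P(Bin(108 − k, 0.45) ≤ 41);
- simple exclusion: the same Z-test with its cut-off recomputed on 108 − k.

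| k | Expected observed rate, 45%·(108 − k)/108 | False non-inferiority, written rule | Cut-off, resected only | False non-inferiority, resected only |
|---|---|---|---|---|
| 0 | 45.0% | 8.4% | 41/108 | 8.4% |
| 1 | 44.6% | 9.8% | 41/107 | 9.8% |
| 2 | 44.2% | 11.3% | 41/106 | 11.3% |
| 3 | 43.8% | 12.9% | 40/105 | 9.2% |
| 4 | 43.3% | 14.8% | 40/104 | 10.7% |
| 5 | 42.9% | 16.8% | 39/103 | 8.7% |

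At k = 1 or 2 the cut-off is still 41 events, so the two rules always agree. Replacing unresected patients until 108 are resected gives 8.4% whatever k is.

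**Step 4: the same data under both denominators.** Take 41 events and three unresected patients. As 41/108, z = −1.470 and the trial passes. As 41/105, z = −1.226 and it fails.

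**Step 5: how often the decision turns on the denominator at a true 45%.** k = 3: 12.9% − 9.2% = 3.7%. k = 5: 16.8% − 8.7%, which is 8.2% before rounding.

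**The case against.** The strongest reply is that the plan already requires surgery. Resection is section 7.2, under Protocol Treatment, so the 120 days post-treatment in section 16.2.1 may start at surgery, and an unresected patient would never complete them. Section 16.2.2 points the same way: an allowance for patients lost because of the 120-day endpoint has little purpose if everyone who began treatment counts regardless of outcome.

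This shows a probable intent, and it stands as far as that. It does not cure the text. Sections 16.1.1 and 16.3.1.1 both state the evaluability rule outright, the estimator uses it, and no section says that it gives way. The timeline does not settle the clock either. Section 16.2.3 says "The final analysis can begin as soon as the last patient has been observed for 4 months post treatment", at about 3 years. Counting from the end of radiation gives 30 + 0.7 + 4 = 34.7 months. Counting from surgery 3 to 7 weeks later gives 35.4 to 36.3 months. Both fit.

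Three stronger readings are tempting and are not supported:
- **That the trial will be biased by a known amount.** k is unknown. Eligibility requires disease judged resectable and non-metastatic, and the interval to surgery is short, so k may be small. At k = 1 or 2, simple exclusion changes no decision.
- **That section 16.3.1.3 bars replacement.** This holds only if the target number is 108. Sections 16.2.2 and 16.5.3 can be read as setting it at 120, which would bring the 12 extra patients inside it.
- **That disagreement between the two denominators at a true rate below 45% is a false conclusion.** At a true 40% the rules differ more often (7.8% at k = 3, 15.8% at k = 5), but the plan defines rates under 45% as non-inferior, so passing there is correct. Only the 45% figures measure the harm.

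It is also fair that a resected-only set conditions on reaching surgery and could drop patients who tolerated radiation worst. The documents do not give the denominator behind the 35% benchmark, so they cannot show which set is like-for-like with it.

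**Conclusion.** The point holds as a fault in the written rule and a conflict between sections. The evaluability sentence and the estimator make an unresected patient a non-event, and the direction favours non-inferiority. Sections 16.2.1 and 16.2.2 hint at a different intent without stating it. The sample size is correct.

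The size depends on an assumed k and on a true rate of exactly 45% among resected patients. Exact false non-inferiority under the written rule first exceeds the nominal 10% at k = 2 and reaches 16.8% at k = 5. The gain from a resected-only denominator starts at k = 3. This should be fixed before the analysis; it does not mean the trial's eventual conclusion will be wrong.

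No rule is given for patients who are resected and then lost before day 120. That is a smaller matter.

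**What to change.** 1. In sections 16.1.1, 16.2.1 and 16.3.1, define the primary set as the first 108 eligible patients who began protocol radiation and underwent the resection, less those section 13.3 declares inevaluable.
2. Run the 120-day clock from surgery in section 16.2.1, and align the wording of 16.2.3.
3. Replace unresected patients from the 12 extra already planned, and state in section 16.3.1.3 that these replacements count toward the 108.
4. Report every unresected patient with the reason, including radiation toxicity, and give the all-treated proportion as a sensitivity analysis. This answers the conditioning on surgery.
5. For resected patients lost before day 120, add two simple sensitivity analyses: counted as events, and excluded. A time-to-event estimator is not needed.

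The cost is protocol and SAP wording, with no planned accrual beyond 120. The downsides are a primary set that conditions on reaching surgery, and a slightly smaller or later analysis if more than 12 patients are ineligible, inevaluable or unresected.

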16.2 Statistical Design

The non-inferiority one-sample test was utilized from PASS software for this design (Non-Inferiority of One Proportion using the Z-Test with S(P0) in PASS 16.0.4). A sample size of 108 evaluable patients achieves 80% power (1-sided significance level of 10%) to detect a non-inferiority margin of 10%, assuming that any major wound complication rate of 45% or above is inferior as compared to the current standard of care complication rate of 35%.⁶ We hypothesize that the proposed hypofractionated preoperative radiation therapy of 42.75 Gy in 15 fractions is not inferior to the conventional fractionation of 50 Gy in 25 fractions

by showing the complication rate is $< 45\%$ for the proposed treatment (non-inferiority margin of 10%).

16.2.1 Decision Rule

After the first 108 eligible patients have completed 120 days post-treatment, we'll do the final analysis of the data, and if the Z-test is significant at the 10% significance level, we'll conclude that hypofractionated preoperative radiation therapy of 42.75 Gy in 15 fractions is not inferior to conventional fractionation of 50 Gy in 25 fractions and can be tested further in larger studies.

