Hypofractionated radiation therapy has been studied to a more limited degree in soft tissue sarcomas. In Poland, a study of hypofractionated preoperative radiation therapy (25 Gy in 5 fractions) was conducted in 272 patients from 2006 to 2011.²¹ This study yielded a higher local failure rate: 19%, with a median follow up of 35 months.²¹ Of note, the biologic effective dose is 34.27 Gy₁₀ with this regimen compared to 43.83 Gy₁₀ with conventional fractionation, suggesting a higher biologic effective dose is needed with hypofractionation to achieve optimal outcomes. Another preoperative hypofractionated study from University of California Los Angeles studied 28 Gy in 8 fractions (biologic effective dose of 32.63 Gy₁₀).²² The local failure rate at 3 years was 11%.²² Again, these results suggest a higher total radiation dose is needed for efficacy when utilizing a hypofractionated radiation treatment course in soft tissue sarcomas.

We propose conducting a single arm, prospective study to evaluate the efficacy and safety of a preoperative hypofractionated course, 42.75 Gy in 15 fractions, for localized, extremity and superficial trunk soft tissue sarcomas. The biologic equivalent dose of this regimen is 45.20 Gy₁₀, similar to 43.83 Gy₁₀ associated with conventionally fractionated 50 Gy in 25 fractions. The primary aim of the study is to determine acute wound complications rates, as defined by O'Sullivan et. al.⁶ Secondary aims will analyze local failure rate, disease-free survival, overall survival, patterns of relapse, late toxicities, and quality of life/patient-reported outcomes. We hypothesize a 15 fraction hypofractionated radiation therapy course will be associated with equivalent short-term toxicity rates and oncologic outcomes as compared to historical standards.

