2.2 Secondary Objectives

- 2.2.1 To report the 5-year local failure rate associated with hypofractionated preoperative radiation therapy, 42.75 Gy in 15 fractions.
- 2.2.2 To report the 5-year disease-free survival rate associated with hypofractionated preoperative radiation therapy, 42.75 Gy in 15 fractions.
- 2.2.3 To report the 5-year overall survival rate associated with hypofractionated preoperative radiation therapy, 42.75 Gy in 15 fractions.
- 2.2.4 To report long-term toxicity rates associated with hypofractionated preoperative radiation therapy, 42.75 Gy in 15 fractions.
- 2.2.5 To describe patterns of relapse associated with hypofractionated preoperative radiation therapy, 42.75 Gy in 15 fractions.
- 2.2.6 To describe patient reported outcomes/quality-of-life outcomes with hypofractionated preoperative radiation therapy, 42.75 Gy in 15 fractions.

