16.2.4 Power and Significance Level

Assuming that the number of major wound complications is binomially distributed, the significance level is 0.1 i.e. there is 10% chance of finding hypofractionated preoperative radiation therapy to be effective when it truly is not. The probability of declaring that the proposed radiation therapy warrants further studies (i.e., statistical power) is 80.01%, if the true acute wound complication is $<45\%$.

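### The decision rule and the alpha statement claim more than the wound-complication test shows: 16.2.1 names no endpoint for 'not inferior', and 16.2.4 calls the regimen 'effective'

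*Combined protocol and SAP*

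**What the plan says.** Section 16.1 describes a single-arm phase II trial with a "non-inferiority design approach to assess the rate of major wound complications". Section 16.1.1 defines the endpoint: "The primary endpoint of this trial is the proportion of patients who experience major wound complications within 120 days of surgical resection". Section 16.2 sets the reference rate at 35%, treats 45% or above as inferior, and names the test as "Non-Inferiority of One Proportion using the Z-Test with S(P0) in PASS 16.0.4".

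Section 16.2.1 then gives the decision rule. If the Z-test is significant at the 10% level, the conclusion is that "hypofractionated preoperative radiation therapy of 42.75 Gy in 15 fractions is not inferior to conventional fractionation" and that the regimen can go on to larger studies. The concluding sentence does not name the endpoint.

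Section 16.2.4 explains the significance level of this test as a "10% chance of finding hypofractionated preoperative radiation therapy to be effective when it truly is not".

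Tumour control is secondary. Section 2.2 lists the aim "To report the 5-year local failure rate associated with hypofractionated preoperative radiation therapy". Section 16.3.2.1 estimates the 5-year local failure rate (LFR5) with a 95% interval, or by Kaplan-Meier if patients are censored. The background in section 1.0 states a wider hypothesis, that the regimen "will be associated with equivalent short-term toxicity rates and oncologic outcomes as compared to historical standards".

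**The concern.** A test on one toxicity rate can support a statement about that rate. It cannot support an unqualified statement that one radiation regimen is not inferior to another, and it cannot find a treatment *effective*. In oncology both phrases are normally read as covering tumour control.

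The ambiguity matters here for two reasons. The hypothesis in section 1.0 covers oncologic outcomes as well as short-term toxicity, so the unqualified conclusion could be taken as confirming both halves. And section 16.3 allows results to be released once the last patient has been followed for at least 6 months, long before 5-year local failure is known. A report that quotes 16.2.1 literally would be faithful to the protocol and would still say more than the data show.

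**Working it through.** **1. Reproduce the design.** Inputs from 16.2: P0 = 0.45, P1 = 0.35, one-sided alpha 0.10, power 0.80, standard error at P0.

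n = [(1.2816 × √(0.45 × 0.55) + 0.8416 × √(0.35 × 0.65)) / 0.10]² = [(1.2816 × 0.4975 + 0.8416 × 0.4770) / 0.10]² = 107.95, rounded up to 108.

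At n = 108 the critical proportion is 0.45 − 1.2816 × √(0.45 × 0.55 / 108) = 0.45 − 1.2816 × 0.04787 = 0.3887. Power at 35% is Φ[(0.3887 − 0.35) / √(0.35 × 0.65 / 108)] = Φ(0.842) = 80.01%. Both of the plan's figures reproduce.

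**2. Turn the rule into a count.** 0.38865 × 108 = 41.97.
- 41 events: 41/108 = 38.0%, z = −1.470, significant.
- 42 events: 42/108 = 38.9%, z = −1.277, not beyond −1.2816.

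The rule is therefore 41 or fewer major wound complications in 108 patients. By exact binomial tails, alpha is P(X ≤ 41 | 0.45) = 0.084 and power at 35% is P(X ≤ 41 | 0.35) = 0.774.

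**3. Look for tumour control in the rule.** There is none. For a given wound complication rate, the chance of the 'not inferior' conclusion is the same whatever the local failure rate. The 10% in 16.2.4 is thus the nominal chance of declaring the wound rate below 45% when it is 45%. It is not an error rate for effectiveness.

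**4. Timing.** Section 16.2.3 gives 120 patients at 4 per month = 30 months of accrual, with the final analysis at about 3 years (36 months). The longest possible follow-up from registration is about 36 months, against the 60 needed. Assuming uniform accrual and no losses, follow-up runs from 36 − 30 = 6 months to 36 months, with a median of 21. The share with at least 24 months is (36 − 24)/30 = 40%, and the share with 60 months is nil.

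**5. What the planned LFR5 analysis can say later.** Assuming complete 5-year follow-up of 108 patients:
- 11 failures (10.2%) give an exact 95% interval of 5.2% to 17.5%.
- The interval lies wholly above the 10% of section 1.0 from 18 failures upwards (18/108 = 16.7%, lower limit 10.2%).
- The probability of that is P(X ≥ 18) = 35% if the true rate is 15%, and 77% if it is 19%. These true rates are illustrative.

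**The case against.** The strongest defence is context. Section 16.1 limits the non-inferiority approach to wound complications. Section 16.2, directly before the rule, says that non-inferiority is shown by a complication rate below 45%. The Z-test in 16.2.1 can only be that test. The paragraph in 16.2.4 opens with the binomial distribution of wound complications and ties power to the true wound complication rate. The stated consequence is modest: the regimen can be tested in larger studies, which is where tumour control would be compared. Screening on toxicity first is an ordinary phase II design.

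Most of this stands, and it rules out several stronger readings that a reader might infer:
- *That the trial sets out to claim non-inferiority in tumour control.* Sections 16.1 and 16.2 show otherwise.
- *That no analysis could contradict the oncologic hypothesis.* Section 16.3.2.1 plans LFR5 with an interval, and section 1.0 gives a 5-year figure of 10% or less to read it against. Step 5 shows that this analysis can contradict the hypothesis.
- *That the 19% local failure of an earlier short course is the benchmark.* That series used 25 Gy in 5 fractions, which section 1.0 puts at a biologic effective dose of 34.27 Gy₁₀, against 45.20 for this regimen and 43.83 for conventional treatment. Its median follow-up was 35 months, so 19% is not a 5-year rate.
- *That the regimen would be recommended on toxicity alone.* The plan says only that it can be studied further.
- *That the lack of a concurrent arm is an error.* The single-arm design and the historical comparison are stated openly in sections 1.0 and 16.1.

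The defence does not repair the two sentences. The decision rule is the text a report will cite, and it drops the qualifier. *Effective* is the wrong word for a toxicity test in any context.

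**Conclusion.** The point holds as one of wording and scope in operative text. The design arithmetic is sound. Section 16.2.1 should name the wound complication rate and does not, and 16.2.4 gives the test a meaning that it lacks. The test supports one statement: with 41 or fewer events in 108, the 120-day major wound complication rate is below 45% at the nominal one-sided 10% level.

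The overstatement has no numerical size, because nothing in the sample size, power or test is affected. What is affected is the trial's headline conclusion, at a time when 5-year local failure cannot have been observed in any patient. The timing rests on the plan's own accrual and analysis dates; slower accrual or a later analysis would lengthen follow-up. Because the intended scope can be recovered from 16.1 and 16.2, this is a correction that should be made rather than a flaw that invalidates the design.

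**What to change.** - **16.2.1:** write the conclusion as 'not inferior with respect to the 120-day major wound complication rate (below 45%, against a historical rate of 35%); no conclusion on tumour control follows from this test'.
- **16.2.4:** replace *effective* with 'non-inferior in major wound complication rate'.
- **16.2.1 or 16.3:** state that local failure, disease-free survival and overall survival are descriptive and immature at this analysis.
- **16.3.2.1:** state that any later claim on oncologic outcomes will rest on the LFR5 estimate and 95% interval already planned there, read against the 5-year figure of 10% or less in section 1.0. For that reading LFR5 must be the proportion with failure; the section currently words the numerator as patients free of failure.

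This is a text amendment. It needs no new data, endpoint, patients or tests, and N = 108 with 80.01% power stays as it is. The cost is a narrower headline claim.
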